9.1 Analysis sets

The **Randomized Set** Epoch 2, respectively Epoch 3 will consist of all patients who are randomized in the randomized treatment epoch (Epoch 2), respectively in the randomized withdrawal epoch (Epoch 3). Unless otherwise specified, mis-randomized patients (mis-randomized in IRT) will be excluded from the randomized set. Mis-randomized patients are defined as cases where IRT contacts were made by the site either prematurely or inappropriately prior to confirmation of the patient's final randomization eligibility and no study medication was administered to the patient.

The **Full Analysis Set (FAS)** Epoch 2, respectively Epoch 3 will consist of all randomized patients in the randomized treatment epoch, respectively in the randomized withdrawal epoch who received at least one dose of study drug. Following the intent-to-treat principle, patients will be analyzed according to the treatment they were assigned to at randomization in each epoch.

The **Per-protocol Set** (PPS) Epoch 2 will consist of all patients in the FAS Epoch 2 who do not fulfill any criteria that could potentially confound the interpretation of analyses conducted on the FAS.

The **Safety Set** Epoch 2, Epoch 3, Epoch 4 will consist of all patients that received study treatment in Epoch 2, resp. Epoch 3, resp. Epoch 4 and had at least one post-baseline safety assessment. Patients will be analyzed according to treatment received. Of note, the statement that a subject had no AEs also constitutes a safety assessment.

9.2 Patient demographics and other baseline characteristics

Summary statistics will be provided for demographic and baseline characteristics by study cohort and treatment group in the randomized treatment epoch (Epoch 2), the randomized withdrawal epoch (Epoch 3) and open-label treatment epoch (Epoch 4).

Any significant prior or active medical condition at the time of signing informed consent will be coded using the MedDRA dictionary. These medical conditions will be summarized by primary system organ class and preferred term.

9.3 Treatments

The exposure to investigational treatment (number of doses) and duration of exposure (days) during this study will be summarized by cohort, epoch, treatment group and listed for the Safety Set.

The number and percentage of patients taking concomitant medication, rescue medication will be summarized by cohort, epoch, treatment group and ATC class.

9.4 Analysis of the primary variable(s)

All efficacy evaluations will be performed on the FAS.

9.4.1 Variable(s)

Each cohort (TRAPS, HIDS, crFMF) of the study will have its own primary efficacy variable analyzed separately and independently of the other cohorts. The primary efficacy variable of the randomized treatment epoch (Epoch 2) and for the overall study is the proportion of responders within each cohort, where a responder is defined as a patient who has resolution of its index disease flare at Day 15 and does not experience a new flare during the 16 weeks following randomization.

Resolution of the index flare (initial flare at the time of the randomization) is defined at the Day 15 visit as:

- PGA < 2, and
- CRP within normal range (≤ 10 mg/L) or reduction $\geq 70\%$ from baseline.

Absence of new flares over the first 16 weeks, where new flare is defined from the time of the resolution of the index flare as:

- Physician's Global Assessment (PGA) ≥ 2 , and

- CRP ≥ 30 mg/L.

In the randomized treatment epoch (Epoch 2), patients needing dose escalation in the canakinumab arms, or crossed-over from Placebo arms to canakinumab, or discontinued from the study due to any reason prior to evaluating the primary endpoint will be considered as non-responders.

9.4.2 Statistical model, hypothesis, and method of analysis

The primary hypothesis tested will be the superiority of canakinumab dose (150 mg sc [or 2mg/kg] q4w) relative to placebo with respect to the proportion of responders in the randomized treatment epoch (Epoch 2), where a responder is defined as a patient who has resolution of its index disease flare and does not experience a new flare during the 16 weeks following randomization. The hypothesis within each cohort will be tested at a one-sided 2.5% level.

The statistical hypothesis is that there is no difference in the proportion of patients with responder rate at Week 16 in canakinumab dose 150 mg s.c. (or 2 mg/kg) q4w versus placebo.

Let p_{jk} denote the proportion of responders at Week 16 for treatment group j and cohort k , $k = 1, 2, 3$ for each of the cohorts and $j=0, 1$ where

- 0 corresponds to placebo,
- 1 corresponds to canakinumab 150mg q4w.

The following hypotheses will be tested

- $H_{1k}: p_{1k} - p_{0k} = 0$ versus $H_{A1k}: p_{1k} - p_{0k} > 0$,

In other words:

- H_1 : canakinumab 150mg q4w is not different to placebo with respect to responder rate at Week 16.

Canakinumab treatment group will be compared to placebo with respect to the proportion of responders at Week 16 using the Fisher's exact test. The proportion of responders, as well as the odds ratio and risk difference with corresponding 97.5% confidence interval will be presented.

9.4.3 Handling of missing values/censoring/discontinuations

Patients needing dose escalation in the canakinumab arms, or who crossed-over from placebo arms to canakinumab in the randomized treatment epoch (Epoch 2), or discontinued from the study due to any reason prior to evaluating the primary endpoint will be considered as non-responders.

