5.5.8 Prohibited Treatment

Use of the treatments displayed in [Table 5-1](#) is NOT allowed after Screening.

Table 5-1 Prohibited treatment

Medication	Action to be taken
Corticosteroid maintenance (prednisone equivalent > 0.2 mg/ kg/ day or greater than the maximum of 15 mg/ day for children over 60 kg).	Investigational treatment does not need to be discontinued as a result of this protocol deviation (PD)
Anakinra	Investigational treatment to be discontinued ²
Rilonacept, tocilizumab, rituximab and any other biologics ¹ (investigational or marketed)	Investigational treatment to be discontinued ²
Etanercept, adalimumab, infliximab, or any TNF inhibitor (investigational or marketed)	Investigational treatment to be discontinued ²
Leflunomide, thalidomide, cyclosporine, or i.v. Ig	Investigational treatment to be discontinued ²
Tofacitinib	Investigational treatment to be discontinued ²
6-Mercaptopurine, azathioprine, cyclophosphamide, or chlorambucil	Investigational treatment to be discontinued ²
Intra-articular, peri-articular or intramuscular corticosteroid injections	Investigational treatment to be discontinued ²
Any other investigational non-biological drug	Investigational treatment to be discontinued ²
Any live vaccination ¹	Investigational treatment to be discontinued ²
Treatment for tuberculosis	Investigational treatment to be discontinued

¹ It is recommended not to initiate any live vaccination or biologic treatment until 3 months after the last dose of investigational treatment. Killed or inactivated vaccines may be permitted according to the investigator's discretion.

² Investigational treatments must be permanently discontinued but patient will remain in the study and will be followed-up for safety.

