5.5.9 Discontinuation of study treatment

Patients may voluntarily discontinue investigational treatment for any reason at any time.

The investigator should discontinue investigational treatment for a given patient if, on balance, he/she believes that continuation would be detrimental to the patient's well-being.

Investigational treatment must be discontinued under the following circumstances:

- Emergence of the following adverse events:
 - a. Absolute QTcF > 500 msec, confirmed by repeat ECG measurements

- b. Serious infections combined with neutropenia CTC grades ≥ 1 ($\text{ANC} < 2.0 \times 10^9/\text{L}$)
- c. CKD as per NKF stages ≥ 4 : $\text{eGFR} \leq 29 \text{ mL/min}/1.73 \text{ m}^2$
- d. Confirmed diagnosis of latent or active TB
- e. Onset of any malignancy
- Any of the following laboratory abnormalities:
 - a. Neutropenia CTC Grades ≥ 2 : $\text{ANC} < 1.5 \times 10^9/\text{L}$
 - b. Thrombocytopenia CTC Grade 4: Platelets $< 10.0 \times 10^9/\text{L}$
- Pregnancy
- Use of prohibited treatment as per [Table 5-1](#)
- Any other protocol deviation that results in a significant risk to the patient's safety

The appropriate personnel from the site and Novartis will assess whether investigational treatment should be discontinued for any patient whose treatment code has been broken inadvertently for any reason.

Patients who discontinue investigational treatment should NOT be considered withdrawn from the study. They should return for the assessments indicated by an asterisk (*) in [Table 6-1](#) or [Table 6-2](#). If they fail to return for these assessments for unknown reasons, every effort (e.g. telephone, e-mail, letter) should be made to contact them as specified in [Section 5.5.11](#).

The investigator must also contact the IRT to register the patient's discontinuation from investigational treatment.

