5.5.13 Study completion and post-study treatment

A patient who completes the baseline visit, is randomized to study drug, continues to participate in all required study visits post randomization up to Day 113 and completes all required assessments is considered a study completer. Site personnel will complete the randomized treatment epoch completion form recording the date the patient last took study medication and whether the patient completed or discontinued from the study.

Enrollment in the screening portion of the study will be closely monitored when the 50th patient per cohort has been randomized. Patients still within the screening portion of the study will terminate their participation after the 60th, and last, patient per cohort has been randomized.

The investigator must provide follow-up medical care for all patients who are prematurely withdrawn from the study, or must refer them for appropriate ongoing care. This care does not require any special treatment but it is recommended not to initiate any live vaccination or biologic treatment until 3 months after the last dose of study treatment.

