5.5.14 Early study termination

The study can be terminated at any time for any reason by Novartis. Should this be necessary, the patient should be seen as soon as possible and treated for a prematurely withdrawn patient. The investigator may be informed of additional procedures to be followed in order to ensure that adequate consideration is given to the protection of the patient's interests. The investigator will be responsible for informing the Institutional Review Board/Independent Ethics Committee (IRBs/IECs) of the early termination of the trial.

6 Visit schedule and assessments

[Table 6-1](#) (screening epoch [Epoch 1] and the randomized treatment epoch [Epoch 2]) and [Table 6-2](#) (randomized withdrawal epoch [Epoch 3] and open-label treatment epoch [Epoch 4]) list all of the assessments and indicate with an “x” when the visits are performed.

Patients are to be seen for all visits, preferably on the designated day. The proposed visit day is displayed in [Table 6-1](#) and [Table 6-2](#).

Patients who prematurely withdraw from Epoch 2 for any reason should be scheduled for a visit when all the assessments listed for Day 113 will be performed.

Patients who prematurely withdraw from Epoch 3 for any reason should be scheduled for a visit when all the assessments listed for Day 281 will be performed.

Patients who prematurely withdraw from Epoch 4 for any reason should be scheduled for a visit when all the assessments listed for Day 785 will be performed.

If a patient refuses to return for these assessments or is unable to do so, every effort should be made to contact him/ her by telephone to determine the reason for discontinuation.

At a minimum, patients will be contacted for safety evaluations and a follow-up visit or phone call for SAEs must be performed 30 days following Investigational treatment discontinuation (TD), Premature subject withdrawal (PSW) or 8 weeks after last injection of study drug, whichever is later.

Documentation of attempts to contact the patient should be recorded in the patient record.

**Table 6-1 Assessment schedule:
Screening epoch (Epoch 1) and randomized treatment epoch (Epoch 2)**

Epoch	Screening (Epoch 1)	Randomized treatment epoch (Epoch 2)						
Visit	1	101	102	103	104	105	199 and/ or PSW	Safety follow-up
Week		1	3	5	9	13	17	
Day	-84 to -3	1	15	29	57	85	113	PSW +30 or 8 weeks after last injection¹
Informed consent	X							
Informed consent for pharmacogenetic sampling ²	X							

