Participation in previous study CACZ885D2203/ MPP treatment plan CAC/885D2207M	X							
Demography	X							
Inclusion/Exclusion Criteria	X	X						
Relevant medical history/ current medical conditions	X							
Prior and concomitant medications (including vaccination status)	X	X	X	X	X	X	X	
Surgical and medical procedures	X	X	X	X	X	X	X	
Disease characteristics	X							
Determination of TB status: QuantiFERON [®] -TB Gold in Tube (QFT-GIT) assay, PPD skin test and/ or chest X-ray (as stipulated by local guidelines)	X							
Hepatitis B and C screen	X							
HIV screen	X							

Epoch	Screening (Epoch 1)	Randomized treatment epoch (Epoch 2)							Safety follow-up
		101	102	103	104	105	199 and/ or PSW		
Visit	1	101	102	103	104	105	199 and/ or PSW		
Week		1	3	5	9	13	17		
Day	-84 to -3	1	15	29	57	85	113	PSW +30 or 8 weeks after last injection ¹	
Pregnancy test – Serum* (for females of child bearing potential)	X								
Pregnancy test – Urinalysis (for females of child bearing potential)		X							
Physical examination*	S	S		S	S	S	S		
Height	X				X ³			X ³	
Weight*	X	X	X	X	X	X	X		
Blood pressure and pulse*	X	X	X	X	X	X	X		
Body temperature*	X	X	X	X	X	X	X		
ECG*	X							X	
Index flare onset		X							
PGA	X	X	X	X	X	X	X		
Physician's severity assessment of key disease-specific signs and symptoms		X	X	X	X	X	X		
Review eDiary instructions	S								
PPGA ⁴	X	X	X	X	X	X	X		
AIDAI ⁴	X	X	X	X	X	X	X		
SF-12® (to be completed by patients ≥18 years of age at Baseline)		X		X				X	
CHQ-PF50© (to be completed by patients >5 <18 years of age at Baseline)		X		X				X	

Epoch	Screening (Epoch 1)	Randomized treatment epoch (Epoch 2)							Safety follow-up
		101	102	103	104	105	199 and/ or PSW		
Visit	1	101	102	103	104	105	199 and/ or PSW		
Week		1	3	5	9	13	17		
Day	-84 to -3	1	15	29	57	85	113	PSW +30 or 8 weeks after last injection ¹	
Follow-up visit or phone call for SAEs*									X

TD = Investigational treatment discontinuation

PSW = Premature subject withdrawal

X = assessment to be recorded on clinical data base

S = assessment to be recorded on source documentation

*These assessments are also to be conducted for patients who discontinue

#These assessments are source documentation only and will not be entered into the CRF

¹ To be performed 30 days following Day 113 or PSW or 8 weeks after last injection of investigational drug, whichever is later for all patients **not** entering Epoch 3

² Only applicable for patients > 16 years of age

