6.4 Efficacy

Patients for whom study treatment must be permanently discontinued as detailed in [Section 5.5.9](#) do not need to complete any of the efficacy assessments listed in this Section 6.4.

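### The primary non-responder rule covers leaving the study but not permanently stopping study drug, so a Day 15 resolver who stops drug and has no later PGA counts, as written, as a responder

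*Protocol*

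**What the plan says.** Protocol 9.4.1 defines a responder as a patient whose index flare has resolved at Day 15 and who has no new flare over 16 weeks. It scores as non-responders "patients needing dose escalation in the canakinumab arms, or crossed-over from Placebo arms to canakinumab, or discontinued from the study due to any reason" before the endpoint is evaluated. Protocol 9.4.3, whose third condition is "discontinued from the study due to any reason prior to evaluating the primary endpoint", and SAP 1.2, 1.10.1.1 and 1.10.1.3 repeat these three conditions with small changes of wording. A new flare requires PGA ≥2 and CRP ≥30 mg/L together.

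The protocol treats stopping drug and leaving the study as different events. The glossary says that they may or may not coincide. Section 5.5.9 states: "Patients who discontinue investigational treatment should NOT be considered withdrawn from the study". The footnote to Table 5-1 says, for most prohibited treatments: "Investigational treatments must be permanently discontinued but patient will remain in the study and will be followed-up for safety".

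Assessments after a stop are limited in two ways. Under Section 6.4, patients whose drug must be stopped under 5.5.9 "do not need to complete any of the efficacy assessments listed in this Section 6.4", and that section includes PGA and CRP. Under 5.5.9, patients who stop drug return for asterisked assessments, which the Table 6-1 footnote explains as: "These assessments are also to be conducted for patients who discontinue". The PGA row of Table 6-1 has no asterisk.

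For missing inputs, SAP 1.10.1.1 lets a central CRP replace a missing local one. Two sensitivity analyses in SAP 1.10.1.5 treat a missing CRP at Visit 102 (Day 15) as no resolution. Neither document has a rule for a missing PGA after Day 15.

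**The concern.** After Day 15, response is the absence of an event, and nothing requires the later assessments to exist. If PGA is no longer taken, no flare can be recorded. A patient who resolves by Day 15 and then stops drug, for toxicity or after a prohibited biologic, can pass through to Week 16 as a success with no evidence that the response lasted. The patient has not left the study, so the discontinuation condition does not apply.

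The secondary endpoints raise related questions. For the Week 16 PGA endpoint (H2), the same patient has no Week 16 value and no stated imputation, although SAP 1.10.2.1 includes all randomized patients in that analysis. The same would hold for CRP and SAA at Week 16 (H3, H4) and for Epoch 3 response (H5) only if the relevant assessment is in fact not made after a stop.

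At stake is whether two programmers would score the same patient alike in the single primary test of a 60-patient cohort.

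**Working it through.** **1. Following one patient through the text.** A patient resolves at Day 15, permanently stops drug afterwards, is not up-titrated or crossed over, and stays in the study.

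- Dose escalation or crossover: does not apply.
- Discontinued from the study: does not apply (Protocol 5.5.9).
- New flare recorded: impossible at a visit with no PGA.
- Result as written: responder.

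The gap is narrower than every visit without a PGA. Because a flare needs both components, an observed CRP <30 mg/L rules one out at that visit. The unsupported visits are those with no PGA and with CRP missing or ≥30 mg/L.

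**2. The plan's own numbers.** Protocol Section 4 gives 30 per arm, 60 per cohort and 180 in total, and expects 20% screening failures: 180 / (1 − 0.20) = 225, which matches its figure. The assumed response rates and power are not visible in the public sample-size sections, so the 30 per arm cannot be rederived.

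**3. One patient at the boundary.** The test is a one-sided Fisher's exact test at 2.5% (Protocol 9.4.2). One patient is 1/30 = 3.3 points. The p-value is the hypergeometric tail probability:

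- 11/30 v 3/30: p = 0.0152 (significant)
- 10/30 v 3/30: p = 0.0287 (not significant)

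**4. Rejection probability.** No stopping rate is given. Assume that a share s of an arm are Day 15 resolvers who stop drug without later flare assessment, and treat them as true failures. Scoring them as successes adds s to that arm's rate. The probability is the sum over all a, b of Bin(a; 30, p1) × Bin(b; 30, p0) wherever Fisher p ≤ 0.025.

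No true difference, 10% v 10% (nominal level 2.5%; 0.5% when stops are scored as failures):

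| s | active arm only | both arms |
|---|---|---|
| 2% | 1.1% | 0.6% |
| 5% | 2.9% | 0.9% |
| 10% | 9.5% | 1.1% |

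Power with placebo at 10% and s = 5%:

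| true active rate | stops as failures | active only | placebo only | both |
|---|---|---|---|---|
| 40% | 71% | 83% | 49% | 64% |
| 60% | 98.5% | 99.5% | 94.0% | 97.6% |
| 70% | 99.9% | >99.9% | 99.2% | 99.8% |
| 85% | about 100% | about 100% | about 100% | about 100% |

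All true rates and all values of s are assumptions. The only response rates in the documents are at least 85% (Protocol 1.1), from open-label studies with their own primary endpoints.

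**The case against.** The best defence is that failure was intended. Protocol 5.5.13 says that a patient who attends all required visits "up to Day 113 and completes all required assessments is considered a study completer". Section 6 says: "Patients who prematurely withdraw from Epoch 2 for any reason should be scheduled for a visit when all the assessments listed for Day 113" are to be performed. SAP 1.2 speaks of canakinumab responders keeping their response until Week 16, and the CRP substitution in SAP 1.10.1.1 excludes patients who discontinued. That intention is plausible, but none of these passages says how to score a patient who stops drug and stays in. The Day 113 catch-up visit is for patients who withdraw. Which assessments are required after a stop is the open question. The SAP 1.2 wording also differs by arm: only placebo-responders are described as completing Epoch 2.

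It is also fair that Section 6.4 permits PGA to be omitted rather than forbidding it, and that its waiver covers mandatory stops only. For voluntary stops the gap rests on the missing asterisk.

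The objection on impact stands. The affected patient must meet several conditions at once, and no document says how often that happens. A reader might infer from the 9.5% that the type I error is inflated. The documents do not support this: the figure needs an average of 3 in 30 canakinumab patients and no placebo patients to be affected, at a true rate of 10%, with every one a true failure. With the same share in both arms, rejection stays at or below 1.1%.

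A reader might also infer that H3 to H5 share the defect outright. That cannot be checked: the CRP and SAA rows of Table 6-1 and all rows of Table 6-2 are not visible in the text available.

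**Conclusion.** The point holds for the primary endpoint. As written, the rule gives a success without evidence to a Day 15 resolver who permanently stops drug, is neither up-titrated nor crossed over, and has a later visit with no PGA and with CRP missing or ≥30 mg/L. For H2, the missing Week 16 PGA has no stated handling. For H3 to H5 the point is conditional on whether CRP, SAA or PGA is collected after a stop.

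The size is modest and uncertain. One patient matters only at the significance boundary. If unassessed stoppers are true failures found in the active arm alone, rejection under no effect passes the nominal 2.5% at s = 5% (2.9%), but not at s = 2% (1.1%). If they occur equally in both arms, it stays well below. With s = 5%, power is at least 94% at 60% v 10% and about 100% at 85% v 10% in every scenario. It would be tempting to say that the rule favours canakinumab. The documents do not support that, since they give neither the number of such stops nor their split by arm. This should be fixed because the scoring is ambiguous and the repair is cheap, not because bias has been shown.

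**What to change.** 1. In Protocol 9.4.1 and 9.4.3 and SAP 1.2, 1.10.1.1 and 1.10.1.3, add one rule for every patient in both arms, on or off drug: a patient whose flare status cannot be established at a scheduled visit after Day 15 through Day 113 (Days 29, 57, 85, 113) is a non-responder. An observed PGA <2 or an observed CRP <30 mg/L is enough to rule out a flare at a visit. Limiting the rule to drug stoppers would leave a patient on drug with the same missing data as a responder.
2. In Protocol 9.5.1 and SAP 1.10.2.1, state that a missing Week 16 value counts as non-response for H2, and likewise for H3 and H4 where the value is missing. Use the rule in item 1 for H5 over the Epoch 3 visits.
3. Add a sensitivity analysis that counts every permanent treatment stop as non-response, including patients with observed flare-free data.
4. Reconcile Protocol 5.5.9, 6.4 and 9.4.3 with SAP 1.10.1.3 and 1.10.2.1, so that the assessments expected after a stop and their scoring agree.

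The cost is a few sentences in each document and one extra analysis, with no added patients or visits. Responder rates may be slightly lower, and some flare-free patients with missed assessments will count as failures.
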